#### **4.3. Protocol Deviations**

A by-participant listing will be provided for those participants who did not meet at least 1 eligibility (inclusion or exclusion) criterion, but enrolled in the study. The listing will present the eligibility criterion (or criteria if more than 1 deviation) that participants did not meet and related comments, if collected.

Important protocol deviations occurring after participants entered the study are documented during routine monitoring. A by-participant listing will be provided for those participants with important protocol deviation.

#### **4.4. Assessment of COVID-19 Impact**

Study conduct was not impacted by the novel coronavirus (COVID-19) pandemic. No analyses will be provided for the assessment of COVID-19 impact.

## **5. BASELINE CHARACTERISTICS**

### **5.1. Demographics and Baseline Characteristics**

Participant demographic variables (i.e., age, sex, race, and ethnicity) and baseline characteristics (body weight [in kg], height [in cm], body mass index [BMI; in kg/m^2]) will be summarized by treatment group and overall using descriptive statistics for continuous variables and using number and percentage of participants for categorical variables. The summary of demographic data will be provided for the Safety Analysis Set.

A by-participant demographic listing, including the informed consent date, will be provided by participant ID number in ascending order.

### **5.2. Other Baseline Characteristics**

Other baseline characteristics include:

- Time from CLE diagnosis to enrollment (years)
- CLE disease subtype
- SLE diagnosis (yes/ no)
- Time from SLE diagnosis to enrollment (years)
- CLASI-Activity (CLASI-A) score at baseline
- CLASI-Damage (CLASI-D) score at baseline
- Subject's global assessment (SGA) of CLE activity (mm) at baseline
- Physician's global assessment (PGA) of CLE activity (mm) at baseline

These baseline characteristics will be summarized by treatment group and overall using descriptive statistics for continuous variables and using number and percentage of participants for categorical variables. The summary of these baseline characteristics will be provided for the Safety Analysis Set. No formal statistical testing is planned.

The time from CLE/SLE diagnosis to enrollment will be calculated in years between the date of enrollment and the date of diagnosis, as  $(\text{the date of enrollment} - \text{the date of diagnosis} + 1) / 365.25$ .

A by-participant listing of other baseline characteristics will be provided by participant ID number in ascending order.

### **5.3. Medical History**

Medical history will be collected at screening for disease-specific and general conditions (i.e., conditions not specific to the disease being studied). Both medical history data will not be coded and will be listed only.

## **6. EFFICACY ANALYSES**

### **6.1. Exploratory Efficacy Endpoint**

#### **6.1.1. Definition of Exploratory Efficacy Endpoints**

The exploratory efficacy endpoints include:

#### **6.1.2. Analysis Methods for Exploratory Efficacy Endpoints**

CCI  
[Redacted text block]

## **7. SAFETY ANALYSES**

### **7.1. Adverse Events and Deaths**

#### **7.1.1. Adverse Event Dictionary**

Clinical and laboratory adverse events (AEs) will be coded using the current version of MedDRA. System organ class (SOC), high-level group term (HLGT), high-level term (HLT), preferred term (PT), and lower-level term (LLT) will be provided in the AE dataset.

#### **7.1.2. Adverse Event Severity**

Adverse events are graded by the investigator as Grade 1, 2, 3, 4, or 5 according to toxicity criteria using CTCAE v5.0. The severity grade of events for which the investigator did not record severity will be categorized as “missing” for tabular summaries and data listings. The missing category will be listed last in summary presentation.

#### **7.1.3. Relationship of Adverse Events to Study Drug**

Related AEs are those for which the investigator selected “Related” on the AE CRF to the question of “Related to Study Treatment.” Relatedness will always default to the investigator’s choice, not that of the medical monitor. Events for which the investigator did not record relationship to study drug will be considered related to study drug for summary purposes. However, by-participant data listings will show the relationship as missing.

#### **7.1.4. Serious Adverse Events**

Serious adverse events (SAEs) will be identified and captured as SAEs if the AEs met the definitions of SAEs that were specified in the study protocol. SAEs captured and stored in the clinical database will be reconciled with the SAEs in the Patient Safety database before data finalization.

#### **7.1.5. Treatment-Emergent Adverse Events**

##### **7.1.5.1. Definition of Treatment-Emergent Adverse Events**

Treatment-emergent adverse events (TEAEs) are defined as 1 or both of the following:

- Any AEs with an onset date on or after the study drug start date and no later than 28 days after permanent discontinuation of study drug
- Any AEs leading to premature discontinuation of study drug.

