7. ADVERSE EVENTS AND TOXICITY MANAGEMENT

7.1. Definitions of Adverse Events and Serious Adverse Events

7.1.1. Adverse Events

An AE is any untoward medical occurrence in a clinical study where the subject is administered a study drug, which does not necessarily have a causal relationship with the treatment. An AE can therefore be any unfavorable and/or unintended sign, symptom, or disease temporally associated with the use of a study drug, whether or not the AE is considered related to the study drug. Adverse events may also include pretreatment or posttreatment complications that occur as a result of protocol-specified procedures or special situations (Section 7.1.3).

An AE does not include the following:

- Medical or surgical procedures such as surgery, endoscopy, tooth extraction, and transfusion. The condition that led to the procedure may be an AE and must be reported
- Preexisting diseases, conditions, or laboratory abnormalities present or detected before the screening visit that do not worsen
- Situations where an untoward medical occurrence has not occurred (eg, hospitalization for elective surgery, social and/or convenience admissions)
- Overdose without clinical sequelae (Section 7.1.3)
- Any medical condition or clinically significant laboratory abnormality with an onset date before the ICF is signed and not related to a protocol-associated procedure is not an AE but rather considered to be preexisting and should be documented in the medical history eCRF.

Preexisting events that increase in severity or change in nature after study drug initiation or during or as a consequence of participation in the clinical study will also be considered AEs.

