7.2.2. Assessment of Severity

The severity of AEs will be graded using the Common Terminology Criteria for Adverse Events (CTCAE). For each episode, the highest grade attained should be reported as defined in the CTCAE.

For AEs associated with laboratory abnormalities, the event should be graded on the basis of the clinical severity in the context of the underlying condition; this may or may not be in agreement with the grading of the laboratory abnormality.

If a CTCAE criterion does not exist for the respective AE, the investigator should use the following grade or adjectives: Grade 1 (mild), Grade 2 (moderate), Grade 3 (severe), Grade 4 (life-threatening), or Grade 5 (fatal) to describe the maximum intensity of the AE.

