8.5.2. Adverse Events

Clinical and laboratory AEs will be coded using the Medical Dictionary for Regulatory Activities (MedDRA). System organ class (SOC), high-level group term, high-level term, preferred term (PT), and lower-level term will be attached to the clinical database.

Events will be summarized on the basis of the date of onset for the event. A treatment-emergent AE will be defined as any AE that begins on or after the date of first dose of study drug up to the date of last dose of study drug plus 28 days.

Summaries (number and percentage of subjects) of treatment-emergent AEs (by SOC and PT) will be provided by treatment group. Additionally, AEs by severity, AEs related to study drug, serious AEs, AEs leading to study and drug discontinuation will be summarized.

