#### **7.2.2.1. Treatment-Emergent Laboratory Abnormalities**

Treatment-emergent laboratory abnormalities are defined as values that increase at least 1 toxicity grade from baseline at any postbaseline time point, up to and including the date of last dose of study drug plus 28 days for participants who permanently discontinued study drug. If the relevant baseline laboratory value is missing, any abnormality of at least Grade 1 observed within the time frame specified above will be considered treatment emergent.

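### The TEAE definition has no criterion for an AE that starts before first dose and worsens on drug, so such an event can drop out of the TEAE tables

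*SAP*

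**What the plan says.** SAP 7.1.5.1 gives two limbs, and meeting either is enough: "Treatment-emergent adverse events (TEAEs) are defined as 1 or both of the following". The first is by onset: "Any AEs with an onset date on or after the study drug start date", with an upper limit of 28 days once drug has been permanently stopped. The second carries no onset condition: "Any AEs leading to premature discontinuation of study drug". Protocol 8.5.2 has only the onset rule: "any AE that begins on or after the date of first dose of study drug", up to 28 days after the last dose.

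Three other provisions bear on an event that changes grade over time:

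- Protocol 7.1.1 brings worsening into the AE definition: "Preexisting events that increase in severity or change in nature after study drug initiation" are to be treated as AEs. It gives no rule for their onset date or for opening a new record.
- Protocol 7.2.2 sets the grade: "For each episode, the highest grade attained should be reported as defined in the CTCAE".
- SAP 7.2.2.1, for laboratory values, does count worsening: "values that increase at least 1 toxicity grade from baseline at any postbaseline time point".

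On output, SAP 7.1.6 tabulates TEAEs by treatment group, adds all deaths to that summary, and lists every AE and SAE with a treatment-emergent flag.

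On collection before first dose, the protocol says two things. Section 7.3.2 and Appendix 3 call for all AEs from consent. Section 7.3.1 limits the period before study drug to SAEs and AEs related to mandated procedures.

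**The concern.** The number of subjects with AEs is one of the two primary endpoints (protocol 8.1.2), and the SAP's AE table is restricted to TEAEs. Screening can last up to 28 days, so an AE can begin after consent, still be present at first dose, and become more severe on drug. A reader of the safety table would want to see that event. The plan does not ensure that it is counted.

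The gap also sits badly with the rest of the plan. The protocol regards on-drug worsening as an AE, and the other primary endpoint, laboratory abnormalities, counts a rise of one grade from baseline. The SAP is otherwise cautious: an AE with no recorded relationship is counted as related (7.1.3), and one with a missing onset date and a stop date after first dose is counted as treatment-emergent (7.1.5.2). Yet a fully dated AE that reaches Grade 3 on drug may not be counted. Because SAP 7.7 keeps only limited safety summaries, these rows carry most of the tabulated AE result.

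**Working it through.** The documents give no figure to reproduce here, and no sample size calculation was done. The check applies each rule to test events and then sizes one misclassification.

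Inputs: the two TEAE rules (SAP 7.1.5.1, protocol 8.5.2); planned arms of 8 and 4 (protocol 8.9); 3 participants randomized (SAP 1.3). Assumption for the test: dosing on Days 1 to 28, so the onset window runs from Day 1 to Day 28 + 28 = Day 56.

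| Test event | Protocol 8.5.2 | SAP 7.1.5.1 | SAP with a worsening limb |
|---|---|---|---|
| 1. Onset Day -10 at Grade 1, Grade 3 on Day 8, one record, drug continued | No | No | Yes |
| 2. As 1, but it leads to stopping drug | No | Yes | Yes |
| 3. As 1, but the worsening is entered as a new record with onset Day 8 | Yes | Yes | Yes |

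Event 1 fails the onset limb because Day -10 is before Day 1, and it fails the second limb because drug continues. Under the highest-grade instruction its single record would carry Grade 3 with an onset before dosing. It is then absent from the any-TEAE, Grade 2 or higher, Grade 3 or higher, related and serious rows. Events 1 and 3 are clinically identical; only the way the site enters them differs, and the documents do not say which way is right.

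For comparison, a laboratory value at Grade 1 at baseline and Grade 3 on Day 8 has risen 3 - 1 = 2 grades. This meets the one-grade threshold in SAP 7.2.2.1, so it is treatment-emergent.

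Size: if the participant has no other TEAE qualifying for the row, the row's percentage is too low by 100/n, where n is the arm's size in the Safety Analysis Set.

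- Planned arms: 100/8 = 12.5 points on GS-5718; 100/4 = 25 points on placebo.
- Actual study: the arm split of the 3 is not given. If it is 2 and 1, the shift is 100/2 = 50 or 100/1 = 100 points. If all 3 were in one arm, it is 100/3 = 33.3 points.

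Events exposed: under protocol 7.3.2 and Appendix 3, any AE starting between consent and first dose and still present at dosing. Under protocol 7.3.1, only SAEs and procedure-related AEs in that period.

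**The case against.** The strongest reply is that protocol 7.1.1 already solves the problem. Its time marker is the start of study drug, so an event present during screening that worsens on drug becomes an AE in its own right, can be entered with an on-drug onset, and is counted under both rules. The highest-grade instruction in 7.2.2 does not forbid a second entry, and the CRF Completion Guidelines mentioned in protocol 9.1.7, which are not in these documents, may settle it. This stands in part: the loss is conditional on one record being kept. It does not close the point, because nothing in the protocol or SAP fixes the record or its date.

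Several stronger readings are tempting, and the documents do not support them:

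- That the SAP goes by onset date only. That is true of protocol 8.5.2; the SAP also has the discontinuation limb.
- That every screening AE is exposed. Protocol 7.3.1 points to a much narrower set, and the conflict with 7.3.2 is unresolved.
- That the event disappears. All deaths are tabulated, and every AE is listed, although with a flag saying not treatment-emergent.
- That the error always favours GS-5718. It lowers the count in whichever arm it occurs; a missed placebo event makes GS-5718 look relatively worse.
- That one event shifts a pooled 1-of-3 row. SAP 7.1.6 specifies AE rows by treatment group, with no pooled row.

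It is also fair to say that with 3 participants, no hypothesis testing and an abbreviated report, a reader can go through each AE individually.

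**Conclusion.** The concern holds in a limited form. Neither TEAE rule has a criterion for worsening, and neither document says how an AE that starts before first dose and worsens on drug is to be dated or recorded. If it is kept as one record and does not lead to stopping drug, it is left out of the main TEAE rows.

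The sizes in the check rest on one affected participant with no other TEAE qualifying for the row; those for the actual study also rest on an assumed arm split and on all 3 having been dosed. The documents do not show that such an event occurred, and give no rate at which to expect one. The practical weight is small, but the change is worth making because a primary safety count should not depend on how a site happens to enter the event.

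**What to change.** Add a third limb to SAP 7.1.5.1: an AE that began before study drug start and that, from study drug start until 28 days after drug is permanently stopped, rises in severity or becomes serious. Count it at the worsened grade. Equivalently, state that such worsening is a new record whose onset is the date of the worsening.

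For any AE ongoing at Day 1, ask the site when the highest grade was reached. If the date cannot be recovered, flag the event in the listing and footnote the table. Do not count it automatically, since it may never have worsened on drug.

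Record the difference from protocol 8.5.2 in SAP 7.7. The discontinuation limb already departs from that section, and 7.7 does not say so. If the SAP is already final, its section 1 requires the change to be documented in the CSR. Separately, reconcile protocol 7.3.1 with 7.3.2 and Appendix 3, so that it is clear which AEs should exist before first dose.

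Cost: one SAP sentence, a few queries for 3 participants, and possibly a slightly higher TEAE count.

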#### 7.1.5.2. Incomplete Dates

If the onset date of the AE is incomplete and the AE stop date is not prior to the first dosing date of study drug, then the month and year (or year alone if month is not recorded) of onset determine whether an AE is treatment emergent. The event is considered treatment emergent if both of the following 2 criteria are met:

- The AE onset is the same as or after the month and year (or year) of the first dosing date of study drug, and
- The AE onset date is the same as or before the month and year (or year) of the date corresponding to 28 days after the date of the last dose of study drug

An AE with completely missing onset and stop dates, or with the onset date missing and a stop date later than the first dosing date of study drug, will be considered to be treatment emergent. In addition, an AE with the onset date missing and incomplete stop date with the same or later month and year (or year alone if month is not recorded) as the first dosing date of study drug will be considered treatment emergent.

#### 7.1.6. Summaries of Adverse Events and Deaths

Treatment-emergent AEs will be summarized based on the Safety Analysis Set.

A brief, high-level summary of the number and percentage of participants who experienced at least 1 TEAE in the categories described below will be provided by treatment group. All deaths observed in the study will also be included in this summary.

The number and percentage of participants who experienced at least 1 TEAE will be provided and summarized by treatment group for the following:

- TEAEs
- TEAEs with Grade 3 or higher
- TEAEs with Grade 2 or higher
- TEAE Related to Study Drug
- TEAE Related to Study Drug with Grade 3 or Higher
- TEAE Related to Study Drug with Grade 2 or Higher
- TE Serious AE
- TE Serious AE Related to Study Drug
- TEAE leading to discontinuation of study drug
- TEAE leading to discontinuation of study
- TE AE leading to death (i.e., outcome of death)

Multiple events will be counted only once per participant in each summary.

In addition, data listings will be provided for all AEs and all SAEs indicating whether the event is treatment emergent, and all deaths.

## **7.2. Laboratory Evaluations**

A by-participant listings for laboratory test results will be provided by participant ID number and visit in chronological order for hematology, serum chemistry, and urinalysis separately. Values falling outside of the relevant reference range and/or having a severity grade of 1 or higher on the Common Terminology Criteria for Adverse Events (CTCAE severity grade) will be flagged in the data listings, as appropriate.

No formal statistical testing is planned.

### **7.2.1. Summaries of Numeric Laboratory Results**

Descriptive statistics for laboratory tests will not be provided. Hematology, chemistry and urinalysis results will be listed.

### **7.2.2. Graded Laboratory Values**

The CTCAE v5.0 will be used to assign toxicity grades (0 to 4) to laboratory results for analysis. Grade 0 includes all values that do not meet the criteria for an abnormality of at least Grade 1. For laboratory tests with criteria for both increased and decreased levels, analyses for each direction (i.e., increased, decreased) will be presented separately.

#### **7.2.2.1. Treatment-Emergent Laboratory Abnormalities**

Treatment-emergent laboratory abnormalities are defined as values that increase at least 1 toxicity grade from baseline at any postbaseline time point, up to and including the date of last dose of study drug plus 28 days for participants who permanently discontinued study drug. If the relevant baseline laboratory value is missing, any abnormality of at least Grade 1 observed within the time frame specified above will be considered treatment emergent.

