
Study Procedures/ Frequency:
	
Study visits for all subjects will occur according to the schedule below; details available in Appendix 3.
 
 • Screening: within 28 days prior to Day 1 • Study Treatment Period: Visits at Day 1 and at Weeks 1, 2, and 4 (or early termination, as applicable) • Follow Up: 28 days after the last dose of study drug

Test Product, Dose, and Mode of Administration:
	
115 mg GS-5718, oral, once daily

Reference Therapy, Dose, and Mode of Administration:
	
Placebo to match GS-5718, oral, once daily

Criteria for Evaluation:
 
Safety:
 
Efficacy:
	
Safety will be assessed through adverse event (AE) reporting, clinical laboratory tests, vital sign assessments, physical examinations (complete and symptom-driven), and ECGs at various time points during the study.
 
The efficacy endpoints of this study are as follows:
 
 • Percent change from baseline in CLASI-A score • Absolute change from baseline in CLASI-A score • Proportion of subjects with a $\geq 50\%$ reduction in CLASI-A score relative to baseline • Proportion of subjects with a ≥ 4-point reduction in CLASI-A score relative to baseline • Change from baseline in SLEDAI-2K total score and domains (subjects with SLE only) • Change from baseline in Subject's Global Assessment (SGA) of CLE activity using a visual analog scale (VAS) • Change from baseline in Physician's Global Assessment (PGA) of CLE activity using a VAS

Biomarkers:
 
Pharmacokinetics:
	
Blood and urine samples for assessment of markers of inflammation, immune status, pathway activation, and type I interferon signaling may be analyzed.
 
Skin biopsy samples for assessment of markers of inflammation, immune status, pathway activation, and type I interferon signaling may be analyzed.
 
CCI
 
For all subjects, intensive PK sampling will be performed at the Week 4 visit. PK blood samples will be collected at predose, and at 0.5, 1, 2, 3, 4, and 6 hours postdose.
 
The predose concentration will be utilized to establish the full 24-hour PK profile at steady-state. Plasma concentrations of GS-5718 will be analyzed and PK will be evaluated. The PK of other metabolites may be explored, as applicable.

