8.1.2. Primary Endpoints

- Number of subjects experiencing AEs
- Number of subjects experiencing laboratory abnormalities

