8.5.3. Laboratory Evaluations

Selected laboratory data (using conventional units) will be summarized using only observed data. Data and change from baseline at all scheduled time points will be presented.

Graded laboratory abnormalities will be defined using CTCAE scale.

Incidence of treatment-emergent laboratory abnormalities, defined as values that increase at least 1 toxicity grade from baseline at any time postbaseline up to the date of last dose of study drug plus 28 days, will be summarized by treatment group.

Laboratory abnormalities that occur before the first dose of study drug or after the subject has been discontinued from treatment for at least 28 days will be included in a data listing.

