CLE = cutaneous lupus erythematosus; dsDNA = double-stranded deoxyribonucleic acid; ECG = electrocardiogram; ENA = extractable nuclear antigen; FFPE = formalin-fixed paraffin-embedded; FSH = follicle-stimulating hormone; HBV = hepatitis B virus; HCV = hepatitis C virus; HIV = human immunodeficiency virus; ICF = informed consent form; IFA = indirect fluorescent antibody; IRT = interactive response technology; PBMC = peripheral blood mononuclear cell; PK = pharmacokinetic; RNA = ribonucleic acid; SLE = systemic lupus erythematosus; TB = tuberculosis; TBNK = T cell/B cell/Natural Killer cell; VL = viral load

a All visits are anchored to Day 1 (eg, screening is up to 28 days prior to Day 1, the Week 1 visit is 7 days after Day 1, with a window of plus or minus 2 days)

b The early termination (ET) visit can satisfy the follow up (FU) visit if it takes place ≥ 28 days following the last dose of study drug

c **CCI**

d Intensive plasma PK sampling will occur prior to the dose (≤ 5 min before dose) (at the Week 4 visit) and at 0.5, 1, 2, 3, 4, and 6 hours postdose (collection window: ±5 minutes for the 0.5 and 1 hour PK sample; ± 15 minutes for the other time points)

Appendix 4. Pregnancy Precautions, Definition for Female of Childbearing Potential, and Contraceptive Requirements

1) Definitions

A) Definition of Childbearing Potential

For the purposes of this study, a female born subject is considered of childbearing potential following the initiation of puberty (Tanner stage 2) until becoming postmenopausal unless the subject is permanently sterile or has medically documented ovarian failure.

Women are considered to be in a postmenopausal state when they are ≥ 54 years of age with cessation of previously occurring menses for ≥ 12 months without an alternative cause. In addition, women < 54 years of age with amenorrhea of ≥ 12 months may also be considered postmenopausal if their follicle-stimulating hormone (FSH) level is in the postmenopausal range and they are not using hormonal contraception or hormonal replacement therapy.

Permanent sterilization includes hysterectomy, bilateral oophorectomy, or bilateral salpingectomy in a female subject of any age.

B) Definition of Male Fertility

For the purposes of this study, a male born subject is considered fertile after the initiation of puberty unless the subject is permanently sterile by bilateral orchidectomy or medical documentation.

2) Contraception Requirements for Female Subjects

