### **3.8.3. Analysis Visit Windows**

No analysis visit windows will be derived for this study. The baseline and relevant nominal visits as recorded on the CRF will be used when data are summarized by visit. Any data relating to unscheduled visits will not be assigned to a particular visit or time point. However, the following exceptions will be made:

- An unscheduled visit prior to the first dosing of study drug may be included in the calculation of the baseline value, if applicable.
- Unscheduled visits after the first dose of study drug will be included in determining the maximum postbaseline toxicity grade.
- For participants who prematurely discontinue from the study, early termination (ET) data will be summarized as a separate visit, labeled as “Early Termination Visit”.
- Data collected on a follow-up visit will be summarized as a separate visit and labeled “Follow-up Visit”.
- Data obtained after the follow-up visit or last dose date plus 28 days (whichever is later) will be excluded from the summaries but will be included in the listings.

All records will be listed by collection date.

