#### **7.2.2.2. Summaries of Laboratory Abnormalities**

The graded laboratory abnormalities summaries (number and percentage of participants) for treatment-emergent laboratory abnormalities will be provided by lab test and treatment group; participants will be categorized according to the most severe postbaseline abnormality grade for a given lab test. Treatment-emergent laboratory abnormalities summary will be presented regardless of fasting status.

For all summaries of laboratory abnormalities, the denominator is the number of participants with nonmissing postbaseline values up to 28 days after last dosing date.

A by-participant listing of treatment-emergent laboratory abnormalities will be provided by participant ID number and visit in chronological order. This listing will include all test results that were collected throughout the study for the lab test of interest, with all applicable severity grades displayed.

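### Does ending the laboratory count at last dose + 28 days wrongly drop abnormalities first seen at an on-schedule follow-up draw on days 29 to 33?

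*SAP*

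**What the plan says.** Protocol 8.1.2 names as one of two primary endpoints the "Number of subjects experiencing laboratory abnormalities". Protocol 8.5.3 defines the treatment-emergent ones as grade increases from baseline "at any time postbaseline up to the date of last dose of study drug plus 28 days". It then states that abnormalities seen once a subject has been off treatment for 28 days or more go into a data listing.

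SAP 7.2.2.1 repeats the limit: "up to and including the date of last dose of study drug plus 28 days for participants who permanently discontinued study drug". SAP 7.2.2.2 applies it to the denominator of every laboratory abnormality summary: "the denominator is the number of participants with nonmissing postbaseline values up to 28 days after last dosing date".

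The Protocol Synopsis sets the visit: "Follow Up: 28 days after the last dose of study drug". Appendix 3 allows 5 days either side and schedules chemistry, hematology and urinalysis there. Its footnote b adds that an early termination "visit can satisfy the follow up (FU) visit if it takes place ≥ 28 days following the last dose of study drug".

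SAP 3.8.3 has a general rule on late data: "Data obtained after the follow-up visit or last dose date plus 28 days (whichever is later) will be excluded from the summaries". For adverse events, the onset limit in SAP 7.1.5.1 is "no later than 28 days after permanent discontinuation of study drug".

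**The concern.** The follow-up visit may take place up to 33 days after last dose, yet the laboratory count stops at day 28. Two participants with the same new abnormality at follow-up, one drawn on day 28 and one on day 30, would be treated differently although both attended on schedule. The second would normally have results from Weeks 1, 2 or 4, so would stay in the denominator and be tabulated without that abnormality.

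SAP 3.8.3 seems to point the other way, because it keeps follow-up data in the summaries even when the visit falls after day 28. SAP 7.2.2.1 also speaks only of participants who permanently discontinued drug, which could be read as leaving completers without a limit. If these were real faults, a primary endpoint would depend on appointment scheduling and on which SAP section a programmer followed.

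**Working it through.** There is no planned figure to reproduce: SAP 1.3 states that no sample size calculation was done. The check is day arithmetic followed by a comparison of the rules.

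**1. Anchor of the visit.** Footnote a of Appendix 3 ties all visits to Day 1. For follow-up that would coincide with Week 4, so the Synopsis and Protocol 3.6, which count from last dose, must govern.

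**2. Permitted days.** 28 − 5 = 23 and 28 + 5 = 33, so days 23 to 33 are allowed, which is 11 days. Days 23 to 28 (6 days) fall inside the limit and days 29 to 33 (5 days) outside: 5/11 = 45%. This is a share of the calendar window, not a probability. The target day, 28, is counted.

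**3. Chance that a late draw occurs at all.** The documents give no visit dates, so the share p of late draws is an assumption. For 3 participants the chance of at least one late draw is 1 − (1 − p)³:

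| Assumed p | At least one late draw among 3 |
|---|---|
| 10% | 0.27 |
| 25% | 0.58 |
| 5/11 | 0.84 |

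A late draw is not a changed count. The count changes only if a grade increase first appears, or first worsens, at that draw after earlier draws at Weeks 1, 2 and 4.

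**4. Drug remaining at day 28.** Protocol 1.2.3.2 gives a median half-life of 25 to 33 hours. 28 × 24 = 672 h; 672/33 = 20.4 and 672/25 = 26.9 half-lives. A first abnormality on days 29 to 33 is weak evidence of a drug effect.

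**5. The rules side by side.**

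| Place | Limit | Role |
|---|---|---|
| Protocol 8.5.3 | last dose + 28 days; later values listed | defines the count |
| Protocol 8.2.1.3, 8.5, 8.5.2 | last dose + 28 days | all safety summaries; adverse events |
| SAP 7.2.2.1, 7.2.2.2 | last dose + 28 days | numerator and denominator |
| SAP 7.1.5.1 | 28 days after stopping drug | adverse event onset |
| SAP 3.8.3 | later of follow-up visit and + 28 days | outer bound on data in summaries |

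The first four rows agree. The fifth says what may enter a summary at all, and the specific definition in SAP 7.2.2.1 then decides what is treatment-emergent. A value can pass the outer bound and still not meet the definition. SAP 7.2.1 drops descriptive laboratory statistics, so no by-visit numeric laboratory table exists that could disagree with the treatment-emergent table.

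**6. Completers.** The denominator rule in SAP 7.2.2.2 and the definition in Protocol 8.5.3 are not restricted to those who stopped early. A programmer therefore has a 28-day cut-off for every participant.

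**7. Visibility of late values.** SAP 7.2 lists all hematology, chemistry and urinalysis results, flagging values out of range or of Grade 1 and above. The listing in SAP 7.2.2.2 shows results from the whole study for each affected test.

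**The case for a change.** The best case for a change runs as follows. The endpoint is primary, and the treatment-emergent table is the only laboratory summary left. An adverse event has a recorded onset date, whereas a laboratory abnormality is seen only when blood is drawn, which is a reason to tie its limit to the scheduled visit. For a completer, follow-up is the only planned off-drug draw. Such draws can find things: in the first-in-human study, three of the four Grade 3 laboratory abnormalities were creatine kinase elevations found at follow-up after discharge (Protocol 1.2.3.1). With 3 participants, one uncounted person moves a crude overall proportion by 100/3 = 33 points.

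The day arithmetic stands, and so does the point that the completer wording could be clearer. The rest does not make a defect. The investigator attributed those creatine kinase elevations to exercise or activity, and their visit days are not counted from last dose, so they say nothing about days 29 to 33. The 33 points describe what one event would do, not how likely it is.

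Counting through the follow-up visit would also have costs:

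- It would depart from Protocol 8.5.3.
- It would end the shared 28-day limit of the two primary endpoints, by up to 33 − 28 = 5 days for in-window visits.
- The window would vary with visit date. Footnote b of Appendix 3 gives no upper limit when an early termination visit stands in for follow-up.
- Sponsor personnel are unblinded (Protocol 5.1.2), and SAP 1 records that all 3 participants had already completed or been terminated. Widening a primary count at that stage would be a post hoc choice.

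**Conclusion.** The concern does not hold. That an abnormality first drawn on days 29 to 33 is listed and not counted is the outcome Protocol 8.5.3 prescribes, and SAP 7.2.2.1 and 7.2.2.2 follow it. A fixed 28-day limit, shared with adverse events and equal for every participant, is a defensible choice, and extending it to the visit date is a debatable trade-off with negligible expected gain.

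This rests on reading SAP 3.8.3 as an outer bound, with the specific definition governing. The judgement of small effect assumes that the half-life, measured in healthy volunteers, carries over to these participants. It also rests on a descriptive analysis of 3 participants whose late values are all listed. Actual visit dates are unknown, so whether any draw fell on days 29 to 33 cannot be said. The conclusion does not depend on it.
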